**Virologic failure for SVR12 = On-treatment virologic failure or Relapse12**

Only subjects who have at least one post-treatment HCV RNA value will be included in analyses of relapse. For the analysis of relapse, completion of treatment is defined as a study drug duration of 52 days or greater for Arm A, 77 days or greater for Arm B, and 103 days or greater for Arm C. If the last available post-treatment value is  $\geq$  LLOQ, then the subject will be considered a relapse (i.e., will not require confirmation).

HCV reinfection is defined as confirmed HCV RNA  $\geq$  LLOQ after the end of active treatment in a subject who had HCV RNA  $<$  LLOQ at Final Treatment Visit, along with the post treatment detection of a different HCV genotype, subtype, or clade compared with baseline, as determined by phylogenetic analysis of the NS3 or NS5A, and/or NS5B gene sequences. Reinfection in the case of the same HCV subtype is defined as a clade switch, as indicated by the lack of clustering between the baseline and post-treatment sequences by phylogenetic analysis. If phylogenetic analysis is not possible due to technical difficulties, HCV reinfection may be determined with a confirmed HCV genotype or subgenotype switch by the Versant HCV Genotype Inno-LiPA Assay v2.0 or Sanger assay.

Post-treatment relapse is defined as described earlier (**Relapse12**, **Relapse24**, **Relapseoverall**), and no genotype, subtype, or clade switch compared with baseline as determined by phylogenetic analysis of the NS3 or NS5A gene sequences. If phylogenetic analysis is not possible due to technical difficulties, the subject will be defined as having a post-treatment relapse unless an HCV genotype or subtype switch is confirmed by the Versant HCV Genotype Inno-LiPA Assay v2.0 or Sanger assay.

### **Reasons for SVR12 Non-Response**

Subjects who do not achieve SVR12 (SVR12 non-responders) will be categorized as having:

1. On-treatment virologic failure (see **On-treatment virologic failure** definition);
2. HCV reinfection (see definition described earlier);
3. Relapse12;

4. Prematurely discontinued study drug with no on-treatment virologic failure (defined as any SVR12 non-responder who prematurely discontinued study drug [study drug duration < 52 days for Arm A, < 77 days for Arm B, and < 103 days for Arm C] and did not meet the **On-treatment virologic failure or reinfection** definitions);
5. Missing follow-up data in the SVR12 window (defined as any subject who completed study drug without data in the SVR12 window after applying the imputation rules and not meeting the definitions of [1], [2], [3], or [4]);
6. Other (defined as any SVR12 non-responder not meeting the definitions of [1] – [5]).

#### **Reasons for SVR24 Non-Response**

Subjects who do not achieve SVR24 (SVR24 non-responders) will be categorized as having:

1. On-treatment virologic failure (see **On-treatment virologic failure** definition);
2. HCV reinfection;
3. Relapse12;
4. Relapse24;
5. Prematurely discontinued study drug with no on-treatment virologic failure (defined as any SVR24 non-responder who prematurely discontinued study drug [study drug duration < 52 days for Arm A, < 77 days for Arm B, and < 103 days for Arm C] and did not meet the **On-treatment virologic failure, HCV reinfection, Relapse12, or Relapse24** definitions);
6. Missing follow-up data in the SVR24 window (defined as any subject who completed study drug without data in the SVR24 window after applying the imputation rules and not meeting the definitions of [1], [2], [3], [4], or [5]);

7. Other (defined as any SVR24 non-responder not meeting the definitions of [1] – [6]).

For the reasons for SVR12 and SVR24 nonresponse defined above, subjects are only to be counted in 1 category. Specifically, subjects who were SVR12 or SVR24 nonresponders meeting the definition of HCV reinfection will be counted in the reinfection category regardless of whether they meet the definition of prematurely discontinued study drug, relapse12 or relapse24.

## **10.2 Handling of Multiplicity**

There will be no hypothesis testing for the primary and secondary efficacy endpoints. Therefore, there will be no adjustment for multiple comparisons.

## **10.3 Primary Efficacy Analysis**

The primary efficacy endpoint is the percentage of subjects who achieve SVR12 (HCV RNA < LLOQ 12 weeks after the last actual dose of study drug) based on the overall ITT population across treatment durations, genotypes, and cirrhosis status. The number and percentage of subjects achieving SVR12 will be calculated along with a two-sided 95% CI using the normal approximation to the binomial distribution, unless the number of SVR12 non-responders is less than 5, where the Wilson's score method will be used to calculate the CI instead.

A summary of the reasons for SVR12 non-response (e.g., on-treatment virologic failure, relapse, other) will be provided.

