**Figure 1. Study Schematic**

### 4.3 Sample Size

It is anticipated that approximately 120 HCV GT1 – 6 infected subjects with chronic renal impairment, with compensated cirrhosis or without cirrhosis, who are either HCV TN or TE with IFN or pegIFN with or without RBV, or SOF plus RBV with or without pegIFN will be enrolled in the study. No formal hypothesis is being tested. If the observed SVR12 rate in this study is 97% among 120 HCV GT1 – 6 renally impaired subjects, then the half-width of the 2-sided 95% confidence interval (CI) using the normal approximation to the binomial distribution is 0.031 (nQuery Advisor, Version 8.0, Statistical Solutions, Ltd., Boston, MA).

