## **10.5 Sensitivity Analyses for SVR**

As sensitivity analyses, the number and percentage of subjects in the mITT-VF population achieving SVR12, as applicable, will be summarized along with a two-sided 95% CI using the normal approximation and a two-sided 95% CI using the Wilson's score method.

The two-sided 95% CI using Wilson's score method will also be calculated as a sensitivity analysis for the primary endpoint of SVR12 based on the ITT population.

A listing of subjects excluded from mITT-VF population will be provided.

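### The primary SVR12 interval changes method at 5 non-responders, so a slightly worse result is reported with higher confidence limits, and Section 4.3 gives the precision of a method the rule would not select at 97%

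*SAP*

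**What the plan says.** Section 10.3 of the SAP makes the normal approximation the default: the SVR12 percentage is "calculated along with a two-sided 95% CI using the normal approximation to the binomial distribution, unless the number of" SVR12 "non-responders is less than 5, where the Wilson's score method" is used instead. The method therefore depends on the observed count: Wilson for 0 to 4 non-responders, normal approximation (Wald) for 5 or more.

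Section 4.3 gives the planning precision. If the observed "rate in this study is 97% among 120 HCV GT1 – 6 renally impaired subjects", "the half-width of the 2-sided 95% confidence interval (CI) using the normal approximation to the binomial distribution is 0.031". It adds that no formal hypothesis is tested.

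Section 10.5 states, with no condition on the count: "The two-sided 95% CI using Wilson's score method will also be calculated as a sensitivity analysis for the primary endpoint of" SVR12 in the ITT population. Sections 10.4, 10.6 and 10.7 use Wilson unconditionally for the secondary endpoints, the subgroups and the additional endpoints.

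**The concern.** Near 100% the two methods place the interval differently. Wilson is pulled towards 50%, while Wald is centred on the estimate and can pass 100%. A rule that changes from one to the other at a fixed count can therefore break the ordering of results, so that one more non-responder gives a higher lower limit.

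This matters because the trial is single-arm and tests no hypothesis. The confidence interval is the only formal statement of uncertainty about the primary endpoint, and readers take its lower limit as the lowest plausible response rate. That limit should not rise when the result gets worse.

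There are two linked points. The precision in Section 4.3 is worked out with one method for a scenario in which Section 10.3 selects the other. And below 5 non-responders, the Wilson sensitivity analysis in Section 10.5 repeats the primary analysis and adds nothing to it.

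**Working it through.** **Inputs.** N = 120, observed rate 0.97 and a two-sided 95% level (Section 4.3), so z = 1.96. Switch at 5 non-responders (Section 10.3).

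**Formulas**, with p the observed proportion and n the sample size:
- Wald: p ± z·√(p(1−p)/n).
- Wilson: centre (p + z²/2n)/(1 + z²/n); half-width [z/(1 + z²/n)]·√(p(1−p)/n + z²/4n²).

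**1. The plan's own figure.** 1.96 × √(0.97 × 0.03/120) = 0.0305, which rounds to the stated 0.031. The Wald interval behind it is 93.95% to 100.05%, so its upper limit exceeds 100%.

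**2. What the rule selects at 97%.** 0.97 × 120 = 116.4 responders, or 3.6 non-responders. The nearest attainable counts are 3 and 4, and both select Wilson.

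| Scenario | Wilson 95% CI | Half-width |
|---|---|---|
| p = 0.97 exactly (not attainable) | 92.2% to 98.9% | 0.033 |
| 117/120 (97.5%) | 92.9% to 99.1% | 0.031 |
| 116/120 (96.7%) | 91.7% to 98.7% | 0.035 |

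At p = 0.97 the Wilson interval is asymmetric: it reaches 4.8 points below the estimate (97.0 − 92.2) and 1.9 above it (98.9 − 97.0).

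**3. The rule around the switch, N = 120.**

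| Non-responders | Estimate | Method selected | Reported 95% CI | Wilson at the same count |
|---|---|---|---|---|
| 3 | 97.5% | Wilson | 92.91% to 99.15% | same |
| 4 | 96.7% | Wilson | 91.74% to 98.70% | same |
| 5 | 95.8% | Wald | 92.26% to 99.41% | 90.6% to 98.2% |
| 6 | 95.0% | Wald | 91.10% to 98.90% | 89.5% to 97.7% |

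From 4 to 5 non-responders the lower limit rises by 0.5 point (92.26 − 91.74) and the upper by 0.7 point (99.41 − 98.70). The upper limit at 5 also exceeds that at 3, and the upper limit at 6 exceeds that at 4. With Wilson throughout (last column), both limits fall with each added non-responder.

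**4. Dependence on N.** Both limits rise from 4 to 5 non-responders at every N checked from 90 to 200, so the reversal does not need exactly 120 subjects.

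**5. How likely the switch region is.** With a true rate of 97% and N = 120, the binomial probability of fewer than 5 non-responders is 0.71. The probability of exactly 4 or 5 is 0.19 + 0.14 = 0.33.

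**6. Coverage.** Exact coverage at N = 120, on a grid of true rates from 0.90 to 0.995:

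| | Minimum | Mean | At 0.97 |
|---|---|---|---|
| Switching rule | 90.7% (at 0.911) | 97.0% | 99.7% |
| Wilson throughout | 91.7% | 95.4% | 97.1% |

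Wald throughout covers 87.5% at a true rate of 0.97.

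**The case against.** The strongest reply is that nothing turns on this interval. There is no hypothesis, margin or success threshold, so a shift of 0.5 to 0.7 point cannot change a conclusion. The rule is fixed in advance and leaves no room for choice after the data are seen. With 5 non-responders the reader also sees the estimate fall, the interval widen slightly (half-width 0.0348 to 0.0358) and, under Section 10.5, the Wilson interval of 90.6% to 98.2% beside the primary one. A non-responder need not be a virologic failure either, because Section 10.1 also counts missing data and premature discontinuation. All of this stands, and it limits the severity.

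Three stronger readings are tempting, and the SAP does not support them.
- **Section 4.3 contains a calculation error.** It does not. It names the normal approximation, and 0.031 reproduces. The difference from Wilson is about 0.002 to 0.004 in half-width, and at 117/120 the Wilson half-width also rounds to 0.031. Setting the 4.8-point lower arm against the stated 3.1 would compare one side of an asymmetric interval with a symmetric half-width.
- **The rule under-covers.** It does not do so in the region that matters. Its minimum over the grid is close to Wilson's and lies far from the planned 97%. For true rates of 0.93 to 0.99 its minimum is 94.8%, against 92.6% for Wilson. The switch does protect against the poor coverage of Wald alone.
- **The repeated Wilson analysis in Section 10.5 is an error.** It is a harmless redundancy.

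The reply does not remove the reversal in the primary interval, or the mismatch between the method used for planning and the one the rule selects in the planning scenario.

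**Conclusion.** The point holds as a modest flaw that is worth correcting; it is not a critical one. At N = 120 the primary interval rises from 91.7–98.7% to 92.3–99.4% as non-responders go from 4 to 5, and the switch lies where the plan expects its result. The half-width in Section 4.3 is correct for its named method but describes an interval that Section 10.3 would not report at 97%. The Wilson half-width there is about 0.033 (0.031 at 117/120, 0.035 at 116/120).

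These figures assume an ITT population of about 120, the usual Wilson interval without continuity correction, and, for the probabilities, independent subjects with a true rate of 97%. The reversal itself needs no assumption about the true rate.

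**What to change.** - **Section 10.3:** use Wilson's score interval for the primary SVR12 analysis whatever the number of non-responders, and delete the switch. This matches Sections 10.4, 10.6 and 10.7.
- **Section 10.5:** make the normal-approximation interval for the ITT population the sensitivity analysis, in place of the Wilson interval. It then differs in method from the primary analysis at every count.
- **Section 4.3:** restate the precision on the Wilson basis: about 92.2% to 98.9% at 97% of 120 (half-width 0.033), with 91.7% to 98.7% at the attainable 116/120. Give both limits, because the interval is asymmetric.

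The cost is SAP wording in three sections and a slightly less favourable stated precision. With 5 or more non-responders, the reported primary interval will have lower limits than under the present rule. No new data are needed. The change is best made before the database lock for the primary analysis.

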## **10.4 Secondary Efficacy Analyses**

The secondary efficacy endpoints are:

- The percentage of subjects with HCV on-treatment virologic failure, and
- The percentage of subjects with Relapse12.

For on-treatment virologic failure and post-treatment relapse, the number and percentage of subjects will be calculated along with a two-sided 95% CI using Wilson's score method for the overall ITT population.

## **10.5 Sensitivity Analyses for SVR**

As sensitivity analyses, the number and percentage of subjects in the mITT-VF population achieving SVR12, as applicable, will be summarized along with a two-sided 95% CI using the normal approximation and a two-sided 95% CI using the Wilson's score method.

The two-sided 95% CI using Wilson's score method will also be calculated as a sensitivity analysis for the primary endpoint of SVR12 based on the ITT population.

A listing of subjects excluded from mITT-VF population will be provided.

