### **5.1.2 Modified Intention-to-Treat (mITT) Populations**

Sensitivity analyses of SVR12 as described in Section 10.5 will be performed on the ITT population modified to exclude subjects who did not achieve SVR12 for reasons other than virologic failure (mITT-VF).

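### SAP 10.5 prints a normal-approximation 95% CI for SVR12 in mITT-VF at any failure count, although 10.3 drops that method below 5 non-responders; the Wilson CI beside it limits the harm

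*SAP*

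**What the plan says.** - **SAP 5.1.2** defines mITT-VF as the ITT population "modified to exclude subjects who did not achieve" SVR12 "for reasons other than virologic failure (mITT-VF"). The only non-responders left are virologic failures.
- **SAP 10.5** asks that SVR12 in mITT-VF be reported with "a two-sided 95% CI using the normal approximation and a two-sided 95% CI using" Wilson's score method. Both intervals are always produced. No condition is set on the number of failures, and nothing is said about truncating limits at 100%.
- **SAP 10.3** uses the normal approximation for the primary ITT analysis unless the number of SVR12 "non-responders is less than 5, where the" Wilson interval takes its place.
- **SAP 4.3** gives the precision illustration: if the observed SVR12 "rate in this study is 97% among 120 HCV GT1 – 6 renally impaired subjects", the 95% half-width "using the normal approximation to the binomial distribution is 0.031". It also states "No formal hypothesis is being tested".
- **SAP 10.4, 10.6 and 10.7** use Wilson's method alone for the secondary, subgroup and additional endpoints.

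**The concern.** The plan recognises in 10.3 that the normal approximation is unsuitable when failures are few, but does not carry that over to 10.5. It is needed at least as much there, because removing non-virologic non-responders can only lower the failure count or leave it unchanged. With fewer than 5 non-responders the primary analysis would drop the normal interval, while the sensitivity analysis of the same endpoint, with as few failures or fewer, would still print it.

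At stake is how the mITT-VF table reads. It would show two intervals, both labelled 95%, and the SAP does not say which one governs. In the low-failure range the normal one has the higher lower limit, so it makes virologic efficacy look more certain than the data allow.

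**Working it through.** **Inputs.** N = 120 and SVR12 = 97% (SAP 4.3); threshold of 5 non-responders (10.3); mITT-VF failures are virologic only (5.1.2). The SAP gives no virologic failure rate, so a range of 0.5% to 3% is assumed. If total SVR12 is 97%, 3% is the ceiling.

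**1. The plan's own figure.** Half-width = 1.96 × √(0.97 × 0.03 / 120) = 1.96 × 0.01557 = 0.0305, which rounds to the stated 0.031. Expected non-responders, all causes: 0.03 × 120 = 3.6, already below 5.

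**2. When the normal interval breaks down.** With k failures in n and p = 1 − k/n, the limits are p ± 1.96 × √(p(1 − p)/n). At k = 0 the width is zero. For k > 0 the upper limit exceeds 1 when k < 1.96² × (1 − k/n). At n = 120:
- k = 3: 3.84 × (1 − 3/120) = 3.75, which is above 3, so the limit exceeds 100%.
- k = 4: 3.84 × (1 − 4/120) = 3.71, which is below 4, so it does not.

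The interval is therefore zero-width or over 100% exactly when k is 0 to 3.

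**3. The two intervals side by side, n = 120.**

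| Failures | Normal approximation | Wilson |
|---|---|---|
| 0 | 100.0% to 100.0% | 96.9% to 100.0% |
| 1 | 97.5% to 100.8% | 95.4% to 99.9% |
| 2 | 96.0% to 100.6% | 94.1% to 99.5% |
| 3 | 94.7% to 100.3% | 92.9% to 99.1% |
| 4 | 93.5% to 99.9% | 91.7% to 98.7% |
| 5 | 92.3% to 99.4% | 90.6% to 98.2% |

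At n = 116 and 118 the pattern is the same.

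**4. How likely 0 to 3 failures are if SVR12 is 97%.** Total non-response of 3% is split into virologic and other, with the mITT-VF size equal to 120 minus the others (exact binomial).

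| Share of non-response that is virologic | Zero width | Above 100% | Either |
|---|---|---|---|
| 100% | 3% | 49% | 51% |
| 67% | 9% | 69% | 78% |
| 50% | 16% | 73% | 89% |
| 33% | 30% | 67% | 97% |
| 25% | 41% | 58% | 99% |

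At n = 120 the probability falls below one half once the virologic failure rate exceeds about 3.05%. At 4% it is 29%.

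**5. Coverage.** Exact coverage of the nominal 95% normal interval at n = 118 (an assumed mITT-VF size), for true virologic failure rates of 0.5%, 1%, 1.5%, 2% and 3%, is 45%, 69%, 83%, 91% and 87%. Wilson's is 97% to 98% throughout.

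**The case against.** The strongest answer lies in the same sentence of 10.5: Wilson's interval is mandatory for mITT-VF at every failure count. Section 10.3 reports a single interval and so needs a switch rule to get a usable one. Section 10.5 reports both, so a valid interval always exists and no data-dependent choice is made. Nothing is decided on the result either: no hypothesis is tested, and mITT-VF is a sensitivity set. The ITT result also receives a Wilson interval unconditionally under 10.5, and virologic failure is reported with Wilson intervals under 10.4 and 10.7. A limit above 100% or an interval of zero width would be plain to see on the page. All of this stands and sets the severity.

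Two stronger readings are tempting and are not supported:
- A reader might infer that the mITT-VF result would carry no valid 95% interval, or would state no uncertainty when there are no failures. It would not: next to 100% to 100% the table would show Wilson's 96.9% to 100%.
- A reader might infer that a broken normal interval is simply to be expected. The SAP gives no virologic failure rate, and 4.3 offers 97% as a conditional illustration of precision, not a forecast. The better-than-even chance holds if SVR12 is near 97%, and only just (51%) if every non-response is virologic.

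What the objection does not remove is the inconsistency with 10.3. Having Wilson alongside also means that the normal interval can be dropped without loss.

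**Conclusion.** Wrong as written, low severity. Section 10.5 requires an interval that the plan's own rule in 10.3 would discard at the same failure count, in a population that cannot have more failures than ITT. With 0 failures it has no width; with 1 to 3 it runs above 100%, and its lower limit is too high: by 2.1 percentage points at 1 failure (97.5% against 95.4%) and by 1.8 at 3 failures (94.7% against 92.9%), n = 120. At an SVR12 near 97% the chance of such an interval is about 51% to 99%, as the virologic share of non-response goes from all to a quarter. That share is an assumption.

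The effect is confined to one of two intervals in a sensitivity table. The SVR12 estimate, the denominators, the primary analysis and the Wilson interval for mITT-VF are unaffected.

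**What to change.** In SAP 10.5, do one of the following:
- report only the Wilson interval for mITT-VF, which also matches 10.4, 10.6 and 10.7; or
- keep the normal-approximation interval but apply the rule of 10.3, so that it is omitted when there are fewer than 5 failures in mITT-VF.

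The first is simpler. Either changes one sentence and at most one table column, needs no new data and loses no information. It is best settled before database lock, so that no interval is dropped or truncated after the results are known.

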### **10.5.1 Imputation Approaches**

No imputation methods will be employed other than those described in Section 6.3.

## **10.6 Efficacy Subgroup Analysis**

The percentage of subjects with SVR12 in the ITT population will be calculated with the corresponding two sided 95% Wilson score intervals, for the following subgroups:

- HCV genotype and available subtype (based on final HCV genotype and subtype determination);
- Prior HCV treatment history (TN or TE);
- For TE subjects, type of previous regimen (IFN- or SOF-based);
- Age (< 65 or ≥ 65 years) and (< 75 or ≥ 75 years);
- Sex (male or female);
- Race (White, Black/African-American, Asian, or other) and black race: black or non-black;
- Baseline BMI (< 30, or ≥ 30 kg/m^2);

- Baseline HCV RNA level ( $< 1,000,000$ ;  $\geq 1,000,000$  to  $< 2,000,000$ ; or  $\geq 2,000,000$  IU/mL);
- Baseline fibrosis stage (equivalent to Metavir F0 – F1, F2, F3, or F4);
- Baseline cirrhosis Status (yes/no)
- Baseline platelet count ( $< 90$  or  $\geq 90 \times 10^9/L$ );
- Baseline albumin ( $< 35$  or  $\geq 35$  g/L);
- History of diabetes (yes/no);
- Subject on stable opiate substitution (yes/no);
- For dialysis subjects, dialysis type (hemodialysis, peritoneal dialysis, or other);
- Chronic kidney disease stage at screening (Stage 3b, 4, 5 without dialysis, or 5 requiring dialysis);
- Baseline polymorphisms in NS3 and/or NS5A.

The presence of baseline polymorphisms in the above listed subgroup analyses is defined in Section 10.8.1.

## 10.7 Additional Efficacy Analyses

The following additional efficacy endpoints will be summarized for the ITT population:

- The percentage of subjects with HCV RNA  $< LLOQ$  at each post-baseline visit in the Treatment Period (using data as observed);
- The percentage of subjects with SVR4;
- The percentage of subjects with SVR24;
- The percentage of subjects who relapsed after achieving SVR12 (**Relapse24**).
- The percentage of subjects with virologic failure through Post-Treatment Week 12 (i.e., the SVR12 non-responders due to on-treatment virologic failure or Relapse12)

The number and percentage of subjects meeting each additional efficacy endpoint will be calculated along with a two-sided 95% CI using the Wilson's score method. Imputations for missing data will be performed as described in Section 6.3 for analysis of SVR,

virologic failure, and relapse. The first bulleted endpoint above will be presented using data as observed.

A summary of the subjects who completed treatment and relapsed (defined as **Relapseoverall**) will be prepared displaying the number of subjects relapsing overall and by SVR visit window (within the SVR4, SVR12, SVR24 windows or after SVR24 window), including the subject number and the SVR visit window corresponding to the first HCV RNA value of those indicating the occurrence of relapse. A similar summary will be prepared for subjects who prematurely discontinued treatment and relapsed after having HCV RNA < LLOQ at their Final Treatment Visit. A listing of subjects in the ITT population excluded from the relapse denominator (e.g., study drug duration < 52 days for subjects assigned to 8 weeks of treatment) will be provided, as applicable.

A listing of subject numbers and reasons for non-response to SVR12 will be prepared. A similar summary and listing will be prepared for subjects who do not achieve SVR24 (as defined in Section 10.1).

The concordance between SVR12 and SVR24 will be assessed by the agreement between SVR12 and SVR24 and the positive predictive value (PPV) and negative predictive value (NPV) of SVR12 on SVR24. The agreement between SVR12 and SVR24 is a percentage defined as the number of subjects achieving both SVR12 and SVR24 and the number of subjects where both SVR12 and SVR24 are not achieved. The PPV of SVR12 on SVR24 is the proportion of subjects who achieve SVR24 out of all subjects who achieved SVR12. The NPV of SVR12 on SVR24 is the proportion of subjects who do not achieve SVR24 out of all subjects who did not achieve SVR12.

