## **6.3 Missing Data Imputation**

### **Missing Data Imputation for SVR**

HCV RNA values will be selected for analysis based on the analysis windows defined in Section 6.2.

For analyses of SVR, subjects missing visit values will have backward imputation applied, if possible. For backward imputation, if the nearest HCV RNA value after the SVR window is unquantifiable or undetectable, then it will be used to impute the HCV RNA value in the SVR window. If a subject is missing an HCV RNA value within the appropriate SVR window after performing backward imputation, then this value will be imputed with an HCV RNA value from a local laboratory if present; otherwise, the HCV RNA value will be missing. Subjects with missing HCV RNA data in the analysis window, after imputations, will be imputed as a failure.

Regardless of the imputation method described above, if a subject starts another treatment for HCV, then all HCV RNA values for this subject measured on or after the start date of the new HCV treatment will be excluded from analyses. The subject will be considered a failure for summaries of viral response at all time points after the start of the new HCV treatment.

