## **10.0 Efficacy Analysis**

### **10.1 General Considerations**

#### **General Considerations**

All efficacy analyses will be performed on the ITT population, unless otherwise specified.

Missing data will be imputed as described in Section 6.3 for analyses of the HCV RNA endpoints of SVR.

Plasma HCV RNA levels will be determined for each sample collected by the central laboratory using the Roche COBAS® AmpliPrep/COBAS® TaqMan® HCV Quantitative Test, v2.0. The lower limit of detection (LLOD) and lower limit of quantification (LLOQ) for this assay (regardless of genotype) are both 15 IU/mL.

HCV RNA results that are detectable but not quantifiable are reported as "< 15 IU/ML HCV RNA DETECTED" and those that are undetectable are reported as "HCV RNA NOT DETECTED" in the database.

The notation "HCV RNA < LLOQ" is used to represent all HCV RNA values < 15 IU/mL, including values reported as "HCV RNA NOT DETECTED" or "< 15 IU/ML HCV RNA DETECTED." HCV RNA  $\geq$  LLOQ are all quantifiable values of 15 IU/mL or greater.

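### SVR12/SVR24 concordance inherits the missing-equals-failure rule, so loss after Week 12 lowers the PPV exactly as a late relapse does (minor)

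*SAP*

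**What the plan says.** Section 10.7 plans to describe concordance by the agreement between SVR12 and SVR24 "and the positive predictive value (PPV) and negative predictive value (NPV) of" SVR12 on SVR24. PPV is taken over everyone who achieved SVR12 and NPV over everyone who did not. Agreement is called a percentage, but its denominator is not stated.

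The paragraph does not mention missing data. Three other places settle how they are handled:

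- Section 10.1: "Missing data will be imputed as described in Section 6.3 for analyses of the HCV RNA endpoints of SVR".
- Section 10.7 itself: "Imputations for missing data will be performed as described in Section 6.3 for analysis of SVR". Only the on-treatment HCV RNA endpoint is exempted and reported as observed.
- Section 10.5.1 allows no imputation method beyond Section 6.3.

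Section 6.3 works in steps. An empty SVR window is back-filled from a later sample: "if the nearest HCV RNA value after the SVR window is unquantifiable or undetectable, then it will be used to impute" the missing value. A local-laboratory value is tried next. Then: "Subjects with missing HCV RNA data in the analysis window, after imputations, will be imputed as a failure". A subject who starts new HCV treatment has later values excluded, and "The subject will be considered a failure for summaries of viral response at all time points after the start of the new HCV treatment".

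No observed-data version of the concordance analysis is planned.

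**The concern.** A predictive value of SVR12 for SVR24 is meant to show whether an undetectable or unquantifiable result at Week 12 holds at Week 24. Counting a missing value as failure is cautious for a response rate. In a two-by-two table of SVR12 against SVR24 it has a different effect, because it decides which cell a subject without data falls into:

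- Loss after an achieved SVR12 enters the discordant cell and pulls PPV down.
- Missing data in both windows enters the concordant-failure cell and pushes NPV up, with no virologic information behind it.
- An SVR12 value back-filled from the SVR24 sample is compared with itself.

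At stake is the reading of one descriptive table. A PPV below 100% could be taken for late relapse when it reflects only missed visits.

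**Working it through.** **The plan's own figure.** Section 4.3 assumes the SVR12 "rate in this study is 97% among 120 HCV GT1" to 6 subjects and states that the half-width of the two-sided 95% "confidence interval (CI) using the normal approximation to the binomial distribution is 0.031". Check: 1.96 × √(0.97 × 0.03 / 120) = 0.0305, which rounds to the stated figure. No figure is stated for the concordance analysis.

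**Inputs from the SAP.** N = 120. 0.97 × 120 = 116.4, so about 116 SVR12 responders and 4 non-responders. In Table 2 the SVR12 window is Study Drug End Days 57 to 126 and the SVR24 window is Days 127 to 210. They are adjacent, so the nearest value after an empty SVR12 window is normally the SVR24 sample.

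**Inputs not in the SAP (assumed).** m = SVR12 responders with no SVR24 value after every Section 6.3 step. r = late relapses. Of the 4 non-responders, 2 are taken as virologic failures and 2 as missing in both windows. Agreement is taken over all 120.

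**Step 1: where each pattern falls.** Missing means no sample in that window, no local result and, for SVR24, no later value below LLOQ.

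| SVR12 window | SVR24 window | SVR12 | SVR24 | Counted as |
|---|---|---|---|---|
| < LLOQ | < LLOQ | yes | yes | agreement |
| < LLOQ | confirmed quantifiable | yes | no | disagreement |
| < LLOQ | missing | yes | no | disagreement |
| confirmed quantifiable | any | no | no | agreement |
| missing | < LLOQ | yes (same sample) | yes | agreement |
| missing | confirmed quantifiable | no | no | agreement |
| missing | missing | no | no | agreement |

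Rows 2 and 3 cannot be told apart in the result. Every pattern with an empty SVR12 window counts as agreement.

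**Step 2: formulas.**
- Planned PPV = (116 − m − r)/116. Planned agreement = (116 − m − r + 4)/120.
- Observed-pairs PPV = (116 − m − r)/(116 − m). Observed-pairs agreement = (116 − m − r + 2)/(118 − m).

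Each lost responder costs 1/116 = 0.86 points of planned PPV, the same as one true late relapse.

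**Step 3: results.**

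| m | r | Planned PPV | Observed PPV | Planned agreement | Observed agreement |
|---|---|---|---|---|---|
| 3 | 0 | 113/116 = 97.4% | 113/113 = 100% | 117/120 = 97.5% | 115/115 = 100% |
| 6 | 0 | 110/116 = 94.8% | 110/110 = 100% | 114/120 = 95.0% | 112/112 = 100% |
| 9 | 0 | 107/116 = 92.2% | 107/107 = 100% | 111/120 = 92.5% | 109/109 = 100% |
| 0 | 1 | 115/116 = 99.1% | 115/116 = 99.1% | 119/120 = 99.17% | 117/118 = 99.15% |
| 6 | 1 | 109/116 = 94.0% | 109/110 = 99.1% | 113/120 = 94.2% | 111/112 = 99.1% |

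With nobody lost, the PPVs are equal and planned agreement is very slightly the higher. With losses after Week 12, planned agreement is the lower.

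**Step 4: back-filling.** Suppose 3 of the 116 have SVR12 taken from the SVR24 sample. With m = 6 and r = 1, dropping them changes the observed-pairs PPV from 109/110 to 106/107, both 99.1%. Across the cases examined (m from 0 to 12, r from 0 to 2) the change is about 0.1 point or less.

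**Step 5: NPV.** As planned it is 4/4 = 100%, and 2 of those 4 have no data. On observed pairs it is 2/2 (Wilson 95% interval 34.2% to 100%). Both are near 100% by definition: under Section 10.1 a confirmed quantifiable value by Week 12 also bars SVR24.

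**The case against.** The strongest defence is that nothing in the plan depends on this table. It is one of the additional analyses, no hypothesis is tested, and a single responder definition is used throughout. Durability is also reported elsewhere. Relapse24 requires HCV RNA data in the SVR24 window and gets its own interval. Section 10.1 sorts SVR24 non-responders by reason, with relapse and missing follow-up kept apart, and Section 10.7 adds a by-subject listing. Section 6.3 also tries later samples and local results before declaring failure, so few subjects may be affected. All of this stands. It limits the importance of the point but does not correct the PPV, NPV or agreement as reported. Relapse24 could be 0% while the PPV is 94.8%.

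A further fair objection concerns the remedy. A plain restriction to observed pairs would drop a subject who relapsed and was retreated before Week 24, because the later values are excluded. That would remove a true virologic failure, so the remedy has to provide for it.

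Three stronger readings are tempting, and the SAP supports none of them:

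- A reader might infer that the measures reflect only drop-out and self-agreement and say nothing about prediction. True late relapses still lower the PPV, complete follow-up makes the planned and observed PPVs equal, and back-filling moves the PPV very little.
- A reader might infer that agreement is always inflated. It falls in every worked case with loss after Week 12.
- A reader might infer that Relapse24 is free of the whole problem. It avoids counting a missing SVR24 as failure, but it still starts from subjects who achieved SVR12, and that status may be back-filled.

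**Conclusion.** The point holds as a minor one. As written, loss after Week 12 biases the PPV down by 0.86 points per subject (on 116 SVR12 responders), and missing data in both windows inflates the NPV. Back-filled pairs agree by construction, with little effect on the PPV. Agreement can be biased in either direction and falls when loss after Week 12 dominates.

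The size rests on assumed losses: 3, 6 or 9 subjects without SVR24 data give a PPV of 97.4%, 94.8% or 92.2% where the virologic answer is 100%. The SAP gives no figure for this loss, and at zero loss the PPV bias disappears. The conclusion also rests on reading Sections 6.3, 10.1, 10.5.1 and 10.7 together, since the concordance paragraph does not mention imputation.

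**What to change.** In Section 10.7:

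1. Compute agreement, PPV and NPV in subjects with an observed, non-imputed HCV RNA result in both the SVR12 and SVR24 windows.
2. Keep as failures those with documented virologic failure whose later values are excluded because they started new HCV treatment.
3. Report the number of subjects excluded, by SVR12 status.
4. State the denominator for agreement.

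The version on the full ITT population with imputation may be kept alongside.

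The change is a sentence or two of text and needs no new data. The cost is a slightly smaller denominator. It will not make the NPV informative: that will still rest on very few subjects and stay near 100%, because of how SVR24 is defined.
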